3.2.2 Secondary

- Clinical Global Impression of Improvement (CGI-I) score assessed at each postbaseline timepoint
- Change from baseline to each timepoint assessed in SHAPS scores

BTRX-335140	BlackThorn Therapeutics, Inc.
Clinical Study Protocol Amendment 7	Date: 24Jan2022

- Change from baseline to each timepoint assessed in Hospital Anxiety and Depression Scale (HADS) subscales (ie, anxiety subscale [HADS-A] and depression subscale [HADS-D] scores)
- Change from baseline to each timepoint assessed in Hamilton Anxiety Rating Scale (HAM-A) total score
- Change from baseline to each timepoint assessed in Sheehan Disability Scale (SDS) scores
- Change from baseline to end of study in Clinical Global Impression Scale Severity (CGI-S) scores
- HAMD-17 response rate
- Assessment of safety through the occurrence of TEAEs, SAEs, and adverse events of special interest (AESIs); change from baseline in vital signs measurements, body weights, body mass index (BMI), clinical laboratory test results, C-SSRS scores, Clinical Opiate Withdrawal Scale (COWS) scores; physical examination findings, ECG results, and ophthalmologic examination findings.

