9.3.3.1 Primary Efficacy Analysis

The primary efficacy analysis is a comparison of mean reduction in HAMD-17 scores between BTRX-335140 and placebo at Week 8. The analysis will be conducted using a Mixed-Models Repeated Measures (MMRM) with change from baseline in HAMD-17 score as the dependent variable and will include treatment group, Week, and Week by treatment group interaction as factors, and baseline HAMD-17 score as covariate. Variance estimation will be based on an unstructured covariance matrix. The model-based Week 8 least square (LS) means, standard errors, 95% confidence intervals (CIs), and *p*-values will be reported.

9.3.3.2 Secondary Efficacy Analyses

Similar to the method described above, a MMRM model will be calculated for the change from baseline to each timepoint assessed for comparisons between BTRX-335140 and placebo for the measures listed below. The model-based time points' LS means, standard errors, 95% CIs, and *p*-values will be reported. Alternatively, ANCOVA may be used, as appropriate. The following measures will be analyzed:

- CGI-I
- CGI-S
- SHAPS
- HADS subscales: HADS-A and HADS-D

BTRX-335140	
Clinical Study Protocol Amendment 7	

- HAM-A total score
- SDS

For CGI-I, an additional analysis comparing the percentage of subjects with responses at Week 4 and Week 8 of 'much improved' or 'very much improved' between BTRX-335140 and placebo will be performed using generalized estimating equations (GEE). The model will include treatment, baseline CGI-S score, week, and week by treatment group interaction. An exchangeable working correlation structure will be assumed.

The change from baseline to Week 8 in CGI-S will be estimated using an ANCOVA model, with main effects for treatment group and a covariate adjustment for baseline score.

The response rates (the percentage of subjects with \geq 50% decrease in HAMD-17 from baseline to Week 4 and Week 8) will be compared between BTRX-335140 and placebo-treated groups using Cochran-Mantel-Haenszel test. Additional categories may be explored.

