- HADS. Change from baseline to each timepoint assessed in HADS total score and HADS subscales (ie, anxiety subscale [HADS-A] and depression subscale [HADS-D] scores). The HADS measures levels of anxiety and depression without regards to somatic symptoms (Zigmond and Snaith 1983). This self-report scale consists of 14 items. Seven of the items are used to evaluate anxiety and 7 evaluate depression. Each item on the questionnaire is scored from 0 to 3. Therefore, the anxiety subscale (HADS-A) and the depression subscale (HADS-D) each range from 0 to 21.
- HAM-A. Change from baseline to each timepoint assessed in HAM-A total score. This instrument will be completed based on a semi-structured interview

BlackThorn Therapeutics, Inc.	Statistical Analysis Plan
K2-MDD-201	Version 2.0; 03 June 2022

(Structured Interview Guide for the Hamilton Anxiety Rating Scale [SIGH-A], Williams 1988). The scale consists of 14 items. Each item is rated on a scale of 0 (feeling not present) to 4 (very severe prevalence of the feeling). The HAM-A total score is the sum of the 14 items and the score ranges from 0 to 56 where higher scores indicate more severe anxiety.

- SDS. Change from baseline to each timepoint assessed in SDS scores. SDS is a brief self-rated tool where the subject rates how symptoms of depression have disrupted the 3 domains (related to work/school, social, and family life) on an anchored 10-point visual analogue scale (Sheehan 1983). The SDS total score will be the sum of the 3 individual item scores where higher scores indicate more severe disability related to MDD symptoms.
- CGI-S. Change in Clinical Global Impression of Severity (CGI-S) from baseline to Week 8. The CGI-S is a clinician-rated instrument that measures the severity of depression at the time of assessment. This rating is based upon observed and reported symptoms, behavior, and function in the past 7 days. The score should reflect the average severity level across the 7 days. The CGI-S is scored on a 7-point scale where a score of 1 indicates that the subject is "normal, not at all ill" a score of 4 indicates that the subject is "moderately ill," and a score of 7 indicates that the subject is "among the most extremely ill subjects" (Guy 1976).

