7.1.2 Analysis Visit Window

For efficacy analyses and safety analysis by visit, assessments at scheduled and unscheduled visits will be mapped to the appropriate analysis window as detailed in Table 3 and Table 4. In the event where more than one visit falls in the same analysis window, the following rules will be used in sequence to determine the record that will be analyzed:

- If there is a scheduled visit in the analysis window, then the scheduled visit's data will be used.
- If there is no scheduled visit in the analysis visit window, the data closest to the scheduled day/time visit will be used.
- If there is no scheduled visit in the analysis visit window and there is a tie between the visits with regards to the number of days/hours before and after the scheduled day, the later data will be used.

Visit windows will not apply to listings. All data will be included in subject listings.

Windowing will be applied to the data prior to any missing data calculations.

Confidential

Period	Screening	Baseline	Study Drug Treatment Safety Follow-up					ollow-up
Visit	1	2	3	4	5	6		
	Days –7 to –28	Day 1	Day 15 (±2 d)	Day 29 (±2 d)	Day 43 (±2 d)	Day 57 (±2 d)	Day 71	Day 85
Analysis Visit Name		Baseline *	Week 2	Week 4	Week 6	Week 8	Week 10	Week 12
CGI-I HADS	NA	≤1 Pre- dose	[2, 22]	[23, 36]	[37, 50]	[51, 71]	NA	NA
HAMD-17 HAM-A SHAPS		≤ 1 Pre-						
	NA	dose	NA	[16, 43]	NA	[44, 71]	NA	NA
CGI-S	NA	≤1 Pre- dose	NA	NA	NA	[44, 71]	NA	NA
SDS	NA	≤1 Pre- dose	NA	[23, 36]	[37, 50]	[51, 71]	NA	NA

Table 3Analysis Windows for Efficacy Analyses

* Baseline for analysis visit refers to baseline value for efficacy analysis defined in Section 7.1.5

Period	Screening	Baseline	s	Study Drug Treatment				ollow-
Visit	1	2	3	4	5	6		
	Days -7 to -28	Day 1	Day 15 (±2 d)	Day 29 (±2 d)	Day 43 (±2 d)	Day 57 (±2 d)	Day 71	Day 85
Analysis Visit Name		Baseline	Week 2	Week 4	Week 6	Week 8	Week 10	Week 12
Vital signs Clinical laboratory tests COWS	NA	≤1 Pre- dose	[2, 22]	[23, 36]	[37, 50]	[51, last dose +30]	NA	NA
Body weight ECG	NA	≤1 Pre- dose	NA	[2, 43]	NA	[44, last dose +30]	NA	NA
Standard Ophthalmologic examination	NA	≤1 Pre- dose	NA	[2, 14]	NA	≥ 15	NA	NA
Corneal specular microscopy	NA	≤1 Pre- dose	NA	NA	NA	NA	NA	≥2
C-SSRS	Nominal	≤ 1 Pre- dose	[2, 22]	[23, 36]	[37, 50]	[51, 64]	[65, last dose +30]	NA

Table 4Analysis Windows for Safety Analyses by Visit

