7.4.7 Secondary Endpoint Analysis Methods

Secondary endpoints including the change from baseline to each timepoint assessed for comparisons between BTRX-335140 and placebo for the measures listed below, will be analyzed using an MMRM model for treatment group, week, and week by treatment group interaction as fixed factors and a covariate adjustment for baseline score. For CGI-I, the baseline CGI-I score will not be included as a covariate, as the baseline assessment of CGI-I refers to the comparison with screening visit. For all other measures the baseline score included as a covariate will be the baseline score for that measure. Variance estimation will be based on an unstructured covariance matrix unless there is a lack of convergence in which case a heterogeneous autoregressive variance-covariance structure will be used.

- CGI-I at each post-baseline visit
- Change in SHAPS from baseline at each post-baseline visit
- Change in HADS total score and HADS subscales: HADS-A and HADS-D from baseline at each post-baseline visit
- Change in HAM-A total score from baseline at each post-baseline visit
- Change in SDS from baseline at each post-baseline visit

The response rates (the percentage of subjects with \geq 50% decrease in HAMD-17 from baseline to Week 4 and Week 8) will be compared between BTRX-335140 and placebotreated groups. The response rates, response rate difference and corresponding 95% Wald CI, and Cochran-Mantel-Haenszel p-value will be reported.

The change at Week 8 from baseline in CGI-S will be estimated using an analysis of the covariance (ANCOVA) model with main effects for treatment group and a covariate adjustment for baseline CGI-S score. The model-based LS means, standard errors, 95% CIs, and 2-sided p-values will be reported.

For SDS, analysis will be performed for the three SDS items separately and the SDS total score as the sum of the individual domains. Note that the work/school domain may be not applicable for all subjects and therefore the analysis of SDS total score will be performed for the subjects with all 3 domain scores and the checkbox of "No work or school" is NOT marked. In addition, a sensitivity analysis of SDS total score will be conducted for all subjects, where the SDS total score will be calculated as (sum of social and family life)*30/20 for the subjects for whom the checkbox of "No work or school" is marked.

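### The Week 8 CGI-S comparison is a complete-case analysis: one post-baseline window (Days 44-71), no missing-data method, and subjects who leave earlier drop out of it

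*SAP*

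**What the plan says.** **Endpoint.** Protocol 3.2.2, like the synopsis, lists "Change from baseline to end of study in Clinical Global Impression Scale Severity (CGI-S) scores". Protocol 9.3.3.2 says "The change from baseline to Week 8 in CGI-S will be estimated using an ANCOVA model", and SAP 6.4.1.2 says "Change in Clinical Global Impression of Severity (CGI-S) from baseline to Week 8". Protocol 3.3 defines the end of the study only as a date for the whole trial.

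**Collection.** Both schedules place CGI-S at Screening, Baseline and Visit 6 (Week 8/EOT). Early terminators have an EOT visit within about 2 days of last dose. Protocol 7.6 and 7.8 limit efficacy ratings there to subjects who have remained on study drug.

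**Windowing.** SAP 7.1.2 says "assessments at scheduled and unscheduled visits will be mapped to the appropriate analysis window as detailed in Table 3 and Table 4". The Table 3 row reads "CGI-S NA ≤1 Pre- dose NA NA NA [44, 71] NA NA". It adds "Windowing will be applied to the data prior to any missing data calculations" and, for listings, "Visit windows will not apply to listings. All data will be included in subject listings". The SAP addendum changes only the ophthalmologic windows.

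**Analysis.** SAP 7.4.7: "The change at Week 8 from baseline in CGI-S will be estimated using an analysis of the covariance (ANCOVA) model", with treatment group and baseline CGI-S in the model. SAP 7.4.5 and addendum 5.2.2 specify multiple imputation and LOCF for HAMD-17 only.

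**Population.** SAP 7.2 requires at least one post-baseline HAMD-17 total score for the Efficacy population, with no Week 8 requirement, and uses that population for every efficacy analysis.

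**The concern.** A subject who stops at Week 4 can be in the Efficacy population and contribute Week 4 HAMD-17, HAM-A and SHAPS to their MMRMs. The same subject contributes nothing to the CGI-S model, even if CGI-S was rated at that EOT visit. The set analysed for CGI-S is thus selected after randomization, and the SAP does not say so.

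The plan allows withdrawal both for unsatisfactory effect and for adverse events (Protocol 4.4), so dropout that depends on response and differs between arms is plausible. Those who remain are then not comparable between arms. CGI-S is a named secondary endpoint with a reported confidence interval and p-value, and no sensitivity analysis would reveal the problem.

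**Working it through.** **1. The plan's own figure.** The only design figure nearby is 84% power at two-sided 0.05, in the protocol's summary of changes. No effect size, SD or dropout rate is visible, so it cannot be reproduced. The point does not depend on it.

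**2. Study-day arithmetic.**
- Days 2-43 have no CGI-S window: 43 − 2 + 1 = 42 of the 57 − 2 + 1 = 56 days from Day 2 to Day 57, or 75%.
- With EOT no later than 2 days after last dose, anyone whose last dose is on or before Day 44 − 1 − 2 = Day 41 has an EOT CGI-S outside every window. An EOT rating from Day 44 on counts as Week 8.

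**3. The same early EOT visit, scale by scale (SAP Table 3).**

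| Measure | Windows | EOT on, say, Day 30 |
|---|---|---|
| HAMD-17, HAM-A, SHAPS | 16-43, 44-71 | kept as Week 4, enters MMRM |
| CGI-I | 2-22, 23-36, 37-50, 51-71 | kept as Week 4, enters MMRM |
| CGI-S | 44-71 | listing only |

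**4. Numbers affected (assumed rates).** If 10%, 20% or 30% of 180 terminate before Day 44, the ANCOVA has 180 × 0.9 = 162, 180 × 0.8 = 144 or 180 × 0.7 = 126 subjects. Some of those lost would have no post-baseline HAMD-17 and so would be outside the Efficacy population anyway. The loss relative to that population is smaller by that number.

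**5. Size of the bias (simulation; every input assumed).** 2,000 replicates, 90 per arm, no treatment effect. Baseline SD 0.6 and Week 4 change SD 1.0. Week 8 change = 0.65 × Week 4 change + residual with SD 0.8. Logit of dropout = logit(nominal rate) + slope × Week 4 change, so poor responders leave more often.

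| Nominal dropout (realised) | Slope | Complete-case bias | Bias / SE (SE 0.17) |
|---|---|---|---|
| 10% vs 25% (about 15% vs 30%) | 1.2 | 0.09 | 0.53 |
| 10% vs 25% (about 11% vs 27%) | 0.6 | 0.05-0.06 | 0.29-0.35 |
| 15% vs 20% (about 20% vs 25%) | 1.2 | 0.02-0.03 | 0.12-0.18 |
| 15% vs 15% (about 20% each) | 1.2 | under 0.01 | about 0 |

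The bias favours the arm with more dropout and changes sign when the rates are swapped.

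Check on the SE: the Week 8 SD is √(0.65² + 0.8²) = 1.03. With 90 × 0.85 = 76.5 and 90 × 0.70 = 63 completers, 1.03 × √(1/76.5 + 1/63) = 0.175, close to the simulated 0.17.

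A shift of 0.53 SE gives a two-sided error rate of P(Z > 1.96 − 0.53) + P(Z < −1.96 − 0.53) = 0.076 + 0.006, about 8%. The simulated rate is 8-9%.

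**6. What imputation recovers (first row of the table).** Imputing Week 8 by arm from baseline and the variable that drives dropout leaves bias under 0.01. With a proxy correlated 0.8 with that variable, about 0.04 remains; with 0.6, 0.06-0.07. The SE stays at about 0.17 throughout.

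**The case against.** The strongest reply is that the SAP follows the protocol: Protocol 9.3.3.2 itself specifies a Week 8 ANCOVA for CGI-S. That stands. A reader might infer that the SAP turned an end-of-study endpoint into a Week 8 one. The documents do not support this, because the two definitions already coexist inside the protocol and end of study has no subject-level meaning there.

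Three other readings are also too strong:
- *ANCOVA is the cause.* With one post-baseline window an MMRM of CGI-S would be complete-case too. The cause is the single window plus the absence of a missing-data method.
- *Collected ratings are thrown away.* They stay in the listings, ratings from Day 44 on are analysed, and subjects no longer on drug have no EOT efficacy rating to lose.
- *Imputation removes the bias.* It does so in the simulation only when the imputation model contains the exact driver of dropout. CGI-S is not scheduled at Week 4, so a real model works with proxies.

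It is also fair to say that this is a Phase 2a study without multiplicity adjustment, that no stated objective names global severity, and that CGI-I covers clinician-rated global change with windows from Day 2. This limits the consequence. It does not supply a missing-data method for CGI-S.

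**Conclusion.** The point holds as a cheap improvement to a secondary analysis. From the documents alone, the Week 8 CGI-S ANCOVA uses only subjects rated on Days 44-71, no sensitivity analysis covers the rest, and this does not match the population stated in SAP 7.2.

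The size is conditional. Bias needs dropout that depends on interim response and differs by arm. Under the assumed inputs it runs from about zero (equal dropout) through 0.02-0.03 (nominal 15% vs 20%) to about 0.09 points on a 7-point scale (nominal 10% vs 25%), against an SE of 0.17. The documents give no dropout rate, SD or dropout mechanism, so none of these is a forecast. The primary HAMD-17 analysis is not affected.

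**What to change.** **1. Add to SAP 7.4.7.** For the Efficacy population, multiply impute missing Week 8 CGI-S separately by arm from baseline CGI-S, CGI-I at Weeks 2, 4 and 6, and HAMD-17 at baseline and Week 4. Impute sequentially by visit, since a subject who leaves after Week 4 also lacks Week 6 CGI-I. Fit the same ANCOVA to each data set, combine with Rubin's rules, and report the result alongside the complete-case analysis with the number analysed per arm. The algorithm in SAP Appendix B should not be reused: it draws from the observed arm mean at each visit without predictors, so on average it returns the complete-case difference.

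**2. Leave out two tempting additions.** An early EOT CGI-S is not a usable predictor, because it is seldom observed together with a Week 8 rating and its coefficient can hardly be estimated. Pooling all EOT ratings into Week 8 is close to LOCF and changes the quantity estimated. In an illustration with no drug effect among completers (assumed SD 1.2, 80% of terminators rated), pooling moved the difference from about 0.00 to +0.09 (10% vs 20% early termination) or +0.15 (10% vs 25%).

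**3. Reconcile the endpoint wording** between the synopsis and Protocol 3.2.2 (end of study) and Protocol 9.3.3.2 and SAP 6.4.1.2 (Week 8).

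**Cost.** SAP text and one more imputation model on data already scheduled. The imputed analysis relies on missing at random given those predictors. If the blind has already been broken, it should be labelled post hoc.

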Clinical Study Protocol Amendment 7	

All efficacy endpoints will also be summarized by visit, including change from baseline information.

Statistical Methods: All statistical comparisons will be made at a 2-sided alpha of 0.05. No adjustment for multiplicity is planned. SAS Version 9.4 or higher will be used to analyze data.

Subjects will be analyzed according to randomized treatment assignment for efficacy assessments and according to treatment received for safety assessments.

Primary Efficacy Analysis: The primary efficacy analysis is a comparison of mean reduction in HAMD-17 scores between BTRX-335140 and placebo at Week 8. The analysis will be conducted using a Mixed-Models Repeated Measures (MMRM) with change from baseline HAMD-17 score as the dependent variable and will include treatment group, Week, and Week by treatment group interaction as factors, and baseline HAMD-17 score as covariate. Variance estimation will be based on an unstructured covariance matrix. The model-based Week 8 least square (LS) means, standard errors, 95% confidence intervals (CIs), and *p*-values will be reported.

Secondary Efficacy Analysis: Comparisons between BTRX-335140 versus placebo for the change from baseline in score at each timepoint assessed for the secondary endpoints will be conducted using MMRM analyses as specified above or analysis of covariance (ANCOVA), as appropriate. For CGI-I an additional analysis comparing the percentage of subjects with responses of 'much improved' or 'very much improved' at each timepoint between BTRX-335140 and placebo will be performed using generalized estimating equations (GEE). Response rates for decrease in HAMD-17 (e.g., the percentage of subjects with \geq 50% decrease in HAMD-17 from baseline to Week 4 and Week 8) will be compared between BTRX-335140 and placebo using Cochran-Mantel-Haenszel tests.

Safety Analyses: Safety data, including AEs, safety laboratory results, physical examination results, vital signs, suicidality, COWS scores, ECGs, and ophthalmologic examination findings will be summarized by treatment group and/or listed.

BTRX-335140	
Clinical Study Protocol Amendment 7	

SCHEDULE OF PROCEDURES AND ASSESSMENTS

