4 INTRODUCTION

Detailed descriptions of the methods and presentation of data analyses proposed for BlackThorn Therapeutics, Inc. Protocol K2-MDD-201 (A Phase 2a, Randomized, Double-blind, Placebo-controlled Proof of Concept Study to Evaluate the Effects of Oral BTRX-335140 Versus Placebo in Subjects With Major Depressive Disorder) Amendment 7 Version 8.0 (24 January 2022) are described in the original statistical analysis plan (SAP), version 2.0, 03 June 2022 (hereafter referred to as "the main SAP").

The purpose of this addendum is to provide clarifications to the definitions and methodology related to the analyses described in the main SAP.

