4 INTRODUCTION

The purpose of this statistical analysis plan (SAP) is to provide comprehensive and detailed descriptions of the methods and presentation of data analyses proposed for BlackThorn Therapeutics, Inc. Protocol K2-MDD-201 (A Phase 2a, Randomized, Double-blind, Placebo-controlled Proof of Concept Study to Evaluate the Effects of Oral BTRX-335140 Versus Placebo in Subjects With Major Depressive Disorder) Amendment 7 Version 8.0 (24 January 2022). The statistical methods applied in the design and planned analyses of this study are consistent with the International Council for Harmonisation (ICH) guideline *Statistical Principles for Clinical Trials* (E9) (1998).

This SAP will be finalized before treatment unblinding and final database lock. There are no changes to the planned analyses described in the study protocol in this SAP; any deviations from this SAP will be documented in the clinical study report (CSR).

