7.2 Analysis Populations

The analysis populations are defined as follows:

- The Safety population is defined as all subjects who received study drug and will be used for summaries of safety parameters. Subjects will be analyzed according to treatment received.
- The Efficacy population includes all randomized subjects who received at least 1 dose of study drug, have a baseline HAMD-17 assessment total score, and have at least 1 post-baseline HAMD-17 assessment total score. Subjects will be analyzed according to randomized treatment assignment. This population will be used for the primary analysis and for all other efficacy analyses.
- The Per-Protocol (PP) population includes subjects in the efficacy population except those who experienced an important protocol deviation that is determined to substantially impact efficacy analysis, or did not have a HAMD-17 score at Week 8 analysis visit, or whose compliance at the end of the study was less than 70%. Subjects will be analyzed according to randomized treatment assignment. This population will be used for supportive efficacy analyses. The list of important protocol deviations for PP population will be classified by the sponsor before the final database lock and the unblinding of the study.

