For CGI-I, an additional analysis will be performed to compare the symptom improvement rate, i.e. the percentage of subjects with responses at each post-baseline visit of 'much improved' or 'very much improved' (i.e. CGI-I score ≤2) between BTRX-335140 and placebo. The symptom improvement rate, improvement rate difference and corresponding 95% Wald CI, and Cochran-Mantel-Haenszel p-value will be reported.

BlackThorn Therapeutics, Inc.	Statistical Analysis Plan
K2-MDD-201	Version 2.0; 03 June 2022

For SHAPS, the analyses will be performed for the SHAPS total scores based on both methods of scoring (SHAPS Total Score [14 to 56] and SHAPS Original Total Score [0 to 14]).

In addition, descriptive summaries of each secondary efficacy variable will be generated by treatment group and by visit.

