7.7 Changes in the Conduct of the Study or Planned Analyses

There are no changes to the planned analyses described in the study protocol in this SAP.

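### The SAP swaps the protocol's baseline-adjusted GEE for the CGI-I improvement rate for a per-visit Cochran-Mantel-Haenszel test, while declaring that no planned analysis has changed

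*SAP*

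**What the plan says.** **Protocol, section 9.3.3.2.** The additional CGI-I analysis is described as "comparing the percentage of subjects with responses at Week 4 and Week 8" between the arms, by GEE. The specification is complete: "The model will include treatment, baseline CGI-S score, week, and week by treatment group interaction", with an exchangeable working correlation.

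**Protocol, synopsis (Statistical Methods).** The same comparison is to be made "at each timepoint between BTRX-335140 and placebo will be performed using generalized estimating equations (GEE"). The method agrees with 9.3.3.2, but the visits do not: every timepoint here, Weeks 4 and 8 there.

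**SAP 7.4.7.** For the same additional analysis, at every post-baseline visit: "The symptom improvement rate, improvement rate difference and corresponding 95% Wald CI, and Cochran-Mantel-Haenszel p-value will be reported".

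**SAP 4 and 7.7.** Section 4 says "There are no changes to the planned analyses described in the study protocol in this SAP; any deviations from this SAP" will be recorded in the clinical study report. Section 7.7 repeats: "There are no changes to the planned analyses described in the study protocol in this SAP". The protocol version that the SAP cites is Amendment 7, Version 8.0, the one supplied.

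**SAP addendum.** Its introduction says: "The purpose of this addendum is to provide clarifications to the definitions and methodology related to the analyses described in the main SAP". It revises the baseline rule for the efficacy scales (5.1.2) and the subgroup summaries (5.2.3, 5.2.4), among other items, but says nothing about the method for the CGI-I rate.

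**The concern.** The SAP replaces a model that the protocol specified down to its working correlation, and then states that it has replaced nothing. Three things follow.

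- The reported rate difference, interval and p-value would not come from the protocol's model.
- The disclosure route misses the change. SAP 4 commits the study report to recording departures from the SAP. An analyst who follows SAP 7.4.7 exactly departs from the protocol but not from the SAP, so that commitment is never triggered.
- Planned adjustment for baseline severity is lost. SAP 7.4.7 also drops baseline CGI-I from the CGI-I mixed model, because that rating refers to screening, and puts nothing in its place. With the GEE gone, neither CGI-I comparison in that section adjusts for baseline severity.

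**Working it through.** **1. The texts side by side**

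| Feature | Protocol 9.3.3.2 | Protocol synopsis | SAP 7.4.7 |
|---|---|---|---|
| Method | GEE | GEE | Rates, Wald interval, CMH |
| Visits | Weeks 4 and 8 | Each timepoint | Each post-baseline visit |
| Covariate | Baseline CGI-S | Not stated | None named |
| Use of repeated ratings | Week, week by treatment, exchangeable | Not stated | None; each visit separate |

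On visits the SAP agrees with the synopsis, so its departure is in the method. The protocol's permission to use ANCOVA belongs to the mixed-model comparisons. For responder rates the protocol assigns CMH to HAMD-17 and GEE to CGI-I. GEE appears nowhere in the visible SAP. SAP 7.4.9 is blacked out, but 7.4.7 is complete for this analysis.

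**2. Precision.** The visible documents give no figure to reproduce for this analysis. Assumed inputs: 90 per arm (180 randomised 1:1), Week 8 rates of 40% and 55%, latent lag-1 correlation between visits 0.6, modest baseline prognosis (latent r = 0.3).

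- SD of the unadjusted difference: sqrt(0.55 × 0.45/90 + 0.40 × 0.60/90) = sqrt(0.4875/90) = 0.0736. Simulation gave 0.0736 for the CMH comparison and 0.0715 for a four-visit GEE.
- Power = Φ(0.15/SD − 1.96): Φ(0.078) = 0.531 against Φ(0.138) = 0.555.
- With 20% random dropout, SDs 0.0821 and 0.0791: Φ(−0.133) = 0.447 against Φ(−0.064) = 0.475.

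The gain is 2.4 to 2.8 points. A separate simulation (400 trials per scenario, about 4% dropout per visit) gave 66% for CMH and 68% for GEE under an effect, and 6.0% and 5.3% under none. The two methods reached different significance verdicts in about 8% and 5% of trials respectively.

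**3. Bias from dropout.** Assumed: Week 8 rates 40% and 55% (weekly paths 12/24/34/40 and 20/36/48/55 at Weeks 2/4/6/8), correlation 0.6 or 0.8, dropout after Weeks 2, 4 and 6 depending on the last rating. The entries are errors, in percentage points, against the difference with nobody lost. *Non-responder* means not rated improved at the last visit. The GEE columns give absolute size; the four-visit column omits Week 2 leavers.

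| Dropout per visit | CMH, Week 8 observed cases | GEE, four visits | GEE, Weeks 4 and 8 |
|---|---|---|---|
| Random, 30% drug and 10% placebo overall | −0.01 to +0.10 | | |
| Both arms: 2% responders, 10% non-responders | +0.19 to +0.39 | 0.00 to 0.13 | |
| Placebo 2%/10%, drug flat 7% | −1.41 to −2.22 | 0.22 to 0.39 | 0.68 to 0.90 |
| Placebo flat 7%, drug 2%/10% | +1.63 to +2.69 | 0.21 to 0.55 | 0.76 to 1.13 |
| Placebo 0%/15%, drug flat 9% | −2.72 to −4.48 | 0.32 to 0.75 | 1.24 to 1.74 |
| Placebo flat 9%, drug 0%/15% | +3.17 to +5.21 | 0.44 to 1.06 | 1.48 to 2.17 |

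With the shared 2%/10% rule and Week 8 rates of 30% and 45%, or 50% and 65%, the CMH error ran from −0.06 to +0.68. Flat 7% and 9% per visit mean 1 − 0.93³ = 20% and 1 − 0.91³ = 25% lost by Week 8.

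Week 2 leavers are omitted because the SAP Efficacy population must "have at least 1 post-baseline HAMD-17 assessment total score", and the HAMD-17 is scheduled after baseline only at Weeks 4 and 8. Someone who leaves after Week 2 without an early-termination HAMD-17 contributes nothing to either method.

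**The case against.** The CMH is a reasonable analysis. The protocol itself plans it, without naming a stratum, for the HAMD-17 response rate, and states no randomisation strata. The SAP therefore treats its two responder rates alike, and the unstratified test is valid under randomisation. The rate is an additional analysis of a secondary endpoint with no multiplicity control; the listed endpoint, the CGI-I score, is analysed by mixed model in both documents. The larger errors above need dropout driven by response in one arm and unrelated to it in the other. Withdrawal rules are the same for both blinded arms, and the visible documents give no dropout rate. Even the largest error, 5.2 points, is smaller than the SD of the difference (7.4 to 8.2 points). All of this stands, and it limits the weight of the point.

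It does not remove the contradiction. A defensible test is still a change from a specified model, and the SAP denies the change twice.

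A reader might infer more than the documents support:

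- **That the method was chosen after seeing results.** The SAP is to be finalised before unblinding; nothing suggests otherwise.
- **That the switch was concealed.** Each method is stated openly in its own document. The fault is an inaccurate declaration.
- **That the CMH result is biased.** That needs the arm-differing dropout described above, which is assumed.
- **That restoring the protocol model cures such bias.** In the arm-differing rows the Weeks 4 and 8 version leaves 39 to 48% of the error (for example 1.74/4.48 = 39%, 0.68/1.41 = 48%). The four-visit version leaves 12 to 20%.

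**Conclusion.** The mismatch is real and rests on the text alone: a covariate-adjusted repeated-measures GEE in the protocol, a per-visit CMH with no named covariate in the SAP, and two statements that nothing changed. That no covariate is used is read from the SAP's silence; a CMH test can be stratified, but no stratum is named.

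It should be corrected, but its reach is small. The primary analysis and the CGI-I score analysis are unaffected. The average power difference is about 2 to 3 points on assumed inputs, although an individual significance verdict can differ. Bias is negligible under random dropout and at most about 0.7 point under a shared moderate rule. It becomes material only if the link between response and dropout differs by arm. The size of the bias depends on assumed rates, correlations and dropout rules; the existence of the contradiction does not.

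**What to change.** Before unblinding, take one of two routes.

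1. **Restore the GEE in SAP 7.4.7** as protocol 9.3.3.2 specifies it, and keep the rate difference and CMH p-value as supportive. Two points must be settled first:
   - *Visits.* Reconcile Weeks 4 and 8 in protocol 9.3.3.2 with the synopsis and SAP, preferably using all post-baseline ratings (Weeks 2, 4, 6 and 8).
   - *Baseline CGI-S.* The scale is rated at screening and baseline. Protocol 9.1 averages pretreatment efficacy values, SAP 7.1.5 takes the last value before dosing, and addendum 5.1.2 takes the last value before, or within 1 hour of, the first dose. Use the SAP rule as modified by the addendum, and reconcile it with the protocol.
2. **Keep the CMH** and declare and justify the departure in SAP 7.7.

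On either route, correct the no-changes statements in SAP 4 and 7.7. The documents do not show whether unblinding has taken place; if it has, disclose the departure in the clinical study report.

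The cost is some wording and a few lines of code; the ratings are already collected. The drawback of route 1 is that an unweighted GEE is not guaranteed unbiased when dropout depends on response. A standardised rate difference, a convergence fallback, non-responder imputation and baseline CGI-S in the CGI-I mixed model are optional additions, not part of the correction.
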